4.1.3. Extension Period

All participants enrolled who consent to continue into the Extension Period will return to the clinic for follow-up visits approximately every 6 months after the last IP injection (Days 364, 532, and 700). Serious AEs, AESIs, and MAAEs will be monitored throughout the Extension Period.

Blood samples will be collected at Days 364, 532, and 700 for the assessment of antibody-mediated immunogenicity. Blood samples will be collected from the CMI subset participants at Days 364, 532, and 700 for PBMC collection and assessment of cellular immunity. Blood samples collected from all participants at Days 364, 532, and 700 will be used for detection of asymptomatic flavivirus infections. Additional blood samples might also be collected during unscheduled visits for safety and/or immunogenicity purposes, at the discretion of the investigator.

As previously described in Section 4.1.2, in case of signs or symptoms suggesting a flavivirus infection (mostly dengue and Zika in the areas where the study will be performed) during the Extension Period, an additional blood sample will be collected to confirm the diagnosis via specific serology and RT-PCR, and clinical information will be carefully collected to evaluate the severity of the clinical case. Also, special attention will be paid to collect signs or symptoms possibly related to Guillain-Barré syndrome.

4.2. Scientific Rationale for Study Design

The design and dose levels proposed for this study (Study mRNA-1893-P201) are based on accumulated safety and immunogenicity data from the Phase 1 Study mRNA-1893-P101, which involved a total of 120 participants. Group unblinding interim analyses performed at Day 57 (ie, 28 days after the second vaccination) showed a safety profile compatible with a large use of the vaccine candidate and a production of ZIKV-specific nAbs at an SCR ranging from 12.5% (2.7% - 32.4%) to 75% (53.3% - 90.2%) after 1 vaccine administration and from 86.4% (65.1% - 97.1%) to 100% (85.8% - 100%) after the complete 2-dose vaccine administration.

Study mRNA-1893-P201 is intended to confirm the safety and immunogenicity trends observed during the Phase 1 study and aims to select the dose level for the Phase 3 program. Two dose levels, and µg and µg, have been chosen as they appear to give the optimal response at Day 57 in terms of geometric mean titers (GMTs) and SCRs with a similar safety profile. The number of participants (200 per treatment arm with approximately 100 participants per baseline flavivirus serostatus in each treatment arm) planned for enrollment is consistent with a Phase 2 stage clinical study. The collection of solicited ARs and unsolicited AEs following vaccination is consistent with vaccine evaluation studies. Additionally, the 2-year follow-up will provide long-term safety profile information and documentation on the duration of the ZIKV-specific nAb response after a 1- or 2-dose regimen. It may also give the opportunity to evaluate occurrence of flavivirus infections,

ModernaTX, Inc.
Protocol: mRNA-1893-P201, Amendment 3

mostly ZIKV and dengue, as the excontinental US sites are areas with potential for flavivirus circulation. The collection of blood at the given time points and the selection of the assays for the assessment of the ZIKV-specific immune response are based on experience from the preclinical and previous clinical studies.

09 Dec 2021

mRNA-1893

4.3. Justification for the Choice of Study Population

It is anticipated that the specific immune response to a ZIKV vaccine candidate in participants who are baseline seronegative may be different from responses in those who are baseline seropositive for flavivirus. To explore the potential differences in safety and immunogenicity, this study will enroll healthy flavivirus-seronegative and flavivirus-seropositive participants.

Safety and immunogenicity evaluation in adults who are flavivirus seronegative at baseline and the most critical at risk population will confirm appropriateness of the dose selection in a larger number of participants.

As the Phase 1 study was predominantly performed in initially flavivirus-seronegative participants, this Phase 2 study will expand the safety data available in flavivirus-seropositive participants, in order to have enough confidence to administer mRNA-1893 without flavivirus serological knowledge in the large Phase 3 studies.

This Phase 2 study population will also target the age group in which the majority of cases occurred in previous epidemics (18 to 49 years of age) and a slightly older population extending up to 65 years, to account for the case distribution age for neurological sequalae such as Guillain-Barré syndrome that has been described with ZIKV.

4.4. Justification for Dose and Schedule

The 2 dose levels of mRNA-1893 tested in participants will be μ μ μ and μ μ based on the assessment of available safety and immunogenicity data from Study mRNA-1893-P101. The 2 dose levels will be administered as a 2-dose regimen (Treatment Arm A and B) with at least a 28-day interval between vaccinations that seems to give the optimal response. In addition, the μ μ μ dose will be administered as a single-dose regimen (Treatment Arm C) to generate safety and immunogenicity data that could be valuable in emergency situations, in military personnel and traveler populations who might need a rapid response, and also in populations living in endemic areas and with pre-existing immune response for which 1 vaccine administration might be sufficient.

4.5. Justification for the Use of Placebo

Because there are currently no licensed ZIKV vaccines available to be used as reference vaccine, 0.9% sodium chloride solution for injection (United States Pharmacopeia [USP] or British Pharmacopeia [BP]) (normal saline) will be used as placebo to maintain the blinding of the study and to serve as a control for the safety and immunogenicity assessments.

Moreover, to have the same study evaluation time point for primary evaluation with both mRNA-1893 dose regimens relative to the last IP injection, participants randomly assigned to Treatment Arm C will be injected at Day 1 with placebo and will receive mRNA-1893 at Day 29 (Table 6).

Those participants who receive saline placebo will have the same safety follow-up as those who receive the 1-dose or 2-dose mRNA-1893 regimen (Treatment Arm A and Treatment Arm B).

4.6. End of Study Definition

The EOS is defined as completion of the last visit of the last participant in the study or last scheduled procedure as shown in Table 1 and Table 2 for the last participant in the study globally.

Participants who do not consent to continue into the Extension Period will be considered to have completed the study if they have completed the EOS Visit approximately 6 months (Visit 10 [Day 196]) after the last IP injection. Participants who consent to continue into the Extension Period will be considered to have completed the study if they have completed the EOS Visit approximately 24 months (Day 700) after the last IP injection.

5. STUDY POPULATION

The study will enroll approximately 800 adult participants aged 18 through 65 years at baseline, including approximately 400 flavivirus-seropositive participants and 400 flavivirus-seronegative participants, who will receive mRNA-1893 or placebo.

A dengue rapid point-of-care test initially used to stratify study participants has been discontinued. After this protocol amendment, all participants will be stratified based on geographic region, assuming most of the baseline seronegatives will come from continental US sites and the baseline seropositives from Puerto Rico. The confirmation will be done based on flavivirus serology testing (dengue immunoglobulin G [IgG] and immunoglobulin M [IgM], West Nile IgG and IgM) performed on a blood sample collected prior to administration of the first vaccination with a goal of an approximately equal distribution of participants among seronegative and seropositive participants within each treatment group.

The planned participant distribution is presented by treatment arm in Table 7.

	·		
Investigational Product	Baseline Flavivirus-Seronegative Participants	Baseline Flavivirus-Seropositive Participants	Total
mRNA-1893 μg (Treatment Arm A)	100	100	200
mRNA-1893 μg (Treatment Arm B)	100	100	200
mRNA-1893 μg (Treatment Arm C)	100	100	200
Placebo (Treatment Arm D)	100	100	200
Total	400	400	800

Table 7: Participant Distribution by Treatment Arm

Upon completion of all eligibility evaluations, the investigator will review the inclusion/exclusion criteria for each participant to determine if the participant is eligible for enrollment in the study. Participants who meet all eligibility criteria will be enrolled in the study.

5.1. Inclusion Criteria

Participants are eligible to be included in the study only if all the following criteria apply:

1. Male or female participant aged 18 through 65 years at the time of consent.

2. Understands and agrees to comply with the study procedures and provides written informed consent.

- 3. According to investigator assessment, is in good general health and can comply with study procedures.
- 4. Female participants of nonchildbearing potential may be enrolled in the study. Nonchildbearing potential is defined as surgically sterile (history of bilateral tubal ligation, bilateral oophorectomy, hysterectomy) or postmenopausal (defined as amenorrhea for ≥ 12 consecutive months prior to the eligibility evaluation without an alternative medical cause). The follicle-stimulating hormone (FSH) level may be measured at the discretion of the investigator to confirm postmenopausal status.
- 5. Female participants of childbearing potential may be enrolled in the study if the participant:
 1) has a negative pregnancy test at the Eligibility Visit and on the day of the first IP injection, 2) has practiced adequate contraception or has abstained from all activities that could result in pregnancy for at least 28 days prior to the first IP injection, 3) has agreed to continue adequate contraception through 3 months following the last IP injection, and 4) is not currently breastfeeding.

Adequate female contraception is defined as consistent and correct use of a Food and Drug Administration (FDA)-approved contraceptive method in accordance with the product label (Table 16). Examples are as follows:

- Barrier method (such as condoms, diaphragm, or cervical cap) used in conjunction with spermicide.
- Intrauterine device.
- Prescription hormonal contraceptive taken or administered via oral (pill), transdermal (patch), subdermal, or IM route.
- Sterilization of a female participant's monogamous male partner prior to entry into the study.

Note: periodic abstinence (eg, calendar, ovulation, symptothermal, post-ovulation methods) and withdrawal are not acceptable methods of contraception.

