Sample Size Determination:

The sample size for this study is not driven by statistical assumptions for formal hypothesis testing. This sample size is regarded as sufficient to provide an understanding of the safety profile of mRNA-1893 and to confirm the dose selection to advance development into future studies.

Approximately 800 participants will be randomly assigned in a 1:1:1:1 ratio to the 4 treatment arms. A total of 600 participants will receive mRNA-1893, 200 participants in each dosing arm, with approximately 100 participants in each flavivirus serostatus cohort and dosing arm; approximately 200 participants will receive placebo. A sample size of 200 (or 400) has at least a 95% probability to observe at least 1 participant with an AE at a true 1.49% (or 0.75%) AE rate.

For the comparison of immunogenicity, the sample size will provide adequate statistical power (approximately 90%) to detect a large effect size (4-fold or above in ZIKV-specific nAb titers, as measured by PRNT50 at Day 57) under reasonable assumptions.

Inclusion Criteria:

Participants are eligible to be included in the study only if all the following criteria apply:

- 1. Male or female participant aged 18 through 65 years at the time of consent.
- 2. Understands and agrees to comply with the study procedures and provides written informed consent.
- 3. According to investigator assessment, is in good general health and can comply with study procedures.
- 4. Female participants of nonchildbearing potential may be enrolled in the study. Nonchildbearing potential is defined as surgically sterile (history of bilateral tubal ligation, bilateral oophorectomy, hysterectomy) or postmenopausal (defined as amenorrhea for ≥ 12 consecutive months prior to the eligibility evaluation without an alternative medical cause). The follicle-stimulating hormone level may be measured at the discretion of the investigator to confirm postmenopausal status.
- 5. Female participants of childbearing potential may be enrolled in the study if the participant: 1) has a negative pregnancy test at the Eligibility Visit and on the day of the first IP injection, 2) has practiced adequate contraception or has abstained from all

activities that could result in pregnancy for at least 28 days prior to the first IP injection, 3) has agreed to continue adequate contraception through 3 months following the last IP injection, and 4) is not currently breastfeeding.

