11.3. APPENDIX 3: Contraceptive Guidance and Collection of Pregnancy Information

11.3.1. Definitions: Women of Childbearing Potential

Females of childbearing potential are those who are considered fertile following menarche and until becoming postmenopausal unless permanently sterile (see below). If fertility is unclear (eg, amenorrhea in adolescents or athletes) and a menstrual cycle cannot be confirmed before first dose of mRNA-1893, additional evaluation should be considered.

Women in the following categories are not considered women of childbearing potential:

- 1. Premenarchal.
- 2. Premenopausal, surgically sterile female with one of the following:
 - a. Documented complete hysterectomy.
 - b. Documented bilateral salpingectomy.
 - c. Documented bilateral oophorectomy.

For individuals with permanent infertility due to an alternate medical cause other than the above, (eg, müllerian agenesis, androgen insensitivity), investigator discretion should be applied to determining study entry.

Note: Documentation can come from the site personnel's review of the participant's medical records, medical examination, or medical history interview.

- 3. Postmenopausal female.
 - A postmenopausal state is defined as no menses for 12 months without an alternative medical cause. The following age-specific requirements apply:
 - O Women < 50 years of age would be considered postmenopausal if they have been amenorrheic for 12 months or more following cessation of exogenous hormonal treatments and if they have luteinizing hormone and FSH levels in the postmenopausal range for the institution.
 - Women ≥ 50 years of age would be considered postmenopausal if they have been amenorrheic for 12 months or more following cessation of all exogenous hormonal treatments, had radiation-induced menopause with last menses > 1 year ago, had chemotherapy-induced menopause with last menses > 1 year ago.
 - A high FSH level in the postmenopausal range may be used to confirm a
 postmenopausal state in women not using hormonal contraception or hormonal

ModernaTX, Inc.
Protocol: mRNA-1893-P201, Amendment 3

09 Dec 2021 mRNA-1893

replacement therapy (HRT). However, in the absence of 12 months of amenorrhea, confirmation with more than one FSH measurement is required.

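### For women under 50, criterion 4 accepts 12 months of amenorrhea alone as postmenopausal, while section 11.3.1 also requires LH and FSH, so the contraception condition can be bypassed

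*Protocol*

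**What the plan says.** Criterion 4 in Protocol 5.1 admits women of nonchildbearing potential, including any woman who is "postmenopausal (defined as amenorrhea for ≥ 12 consecutive months prior to the eligibility evaluation without an alternative medical cause". It has no age condition. The FSH "level may be measured at the discretion of the investigator to confirm postmenopausal status". The synopsis repeats this: "The follicle-stimulating hormone level may be measured at the discretion of the investigator to confirm postmenopausal status". Section 8.2.1 and a Table 1 footnote also leave FSH optional.

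Criterion 5 covers women of childbearing potential only. Among other conditions, the woman must have used contraception or abstained for the 28 days before the first injection, and she is eligible only if she "has agreed to continue adequate contraception through 3 months following the last IP injection".

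Appendix 3 covers the subject twice.
- **Section 11.3.1** defines childbearing potential. It starts from 12 months without menses and then adds: "The following age-specific requirements apply". The first of these reads "Women < 50 years of age would be considered postmenopausal if they have been amenorrheic for 12 months or more" after stopping exogenous hormones, and also "if they have luteinizing hormone and FSH levels in the postmenopausal range for the institution". Where fertility is in doubt and "a menstrual cycle cannot be confirmed before first dose of mRNA-1893, additional evaluation should be considered".
- **Section 11.3.2(a)** returns to a rule without ages: either 12 months of amenorrhea with no other medical explanation, *or* a documented postmenopausal FSH.

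**The concern.** The same protocol gives two answers for the same woman. Her classification decides whether criterion 5 applies to her, and so whether she must use contraception around two injections of an investigational mRNA vaccine. The text that sites use to decide enrollment is the laxer one, and nothing in it points to the stricter one.

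The stake is participant safety. Section 7.1 makes pregnancy a bar to further injections, and 8.6.6 treats abnormal pregnancy outcomes as serious adverse events. The reporting rules would cover such a pregnancy, but only once it is known; contraception is the preventive measure.

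**Working it through.** No figure in the plan needs reproducing. The check sets the texts side by side and then does one short sum.

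**1. Test case.** A woman aged 18 to 49, at least 12 months without menses, no other medical cause found, not permanently sterile, no hormone result. Criterion 1 admits ages 18 through 65, so she is in scope.

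**2. Classification.**

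| Text | Rule applied to her | Result |
|---|---|---|
| 5.1 and synopsis, criterion 4 | 12 months of amenorrhea; FSH optional | Postmenopausal; criterion 5 does not apply |
| 11.3.2(a) | 12 months of amenorrhea *or* FSH | Postmenopausal |
| 11.3.1 | 12 months of amenorrhea *and* LH *and* FSH | Not postmenopausal; criterion 5 applies |

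**3. Can the texts be reconciled?** Section 11.3.1 is not simply extra detail on criterion 4: a test left to discretion cannot also be a requirement. A later bullet in 11.3.1 lets a high FSH confirm postmenopausal status in women not using hormonal contraception or HRT, with no age limit and no LH. That leaves open whether FSH alone could suffice under 50. It does not rescue the test case, because she has no FSH result either.

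**4. Which text operates at enrollment?** Sections 4.1.1, 5 and 8 all decide eligibility on the inclusion and exclusion criteria. Criterion 4 does not mention 11.3.1. The contraception text under criterion 5 does point to Table 16 in Appendix 3, but a site reaches it only after classing the woman as of childbearing potential.

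**5. Length of the period with no contraception requirement, from the first injection.** Inputs: Day 1 to Day 29 is 28 days; Table 1 allows -3/+7 days around Day 29; the synopsis and 4.1 require at least 28 days between injections; 3 months is taken as 91 days (assumption).

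Days = dosing interval + 91.
- Nominal: 28 + 91 = 119.
- Latest in window: (28 + 7) + 91 = 126.
- Earliest in window: (28 - 3) + 91 = 116, but a 25-day interval breaks the 28-day minimum, so if that minimum binds the range is 119 to 126.

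The 28 days before the first injection are an entry condition, not time after exposure, and are left out.

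**6. Pregnancy tests.** Table 1 schedules urine tests on Days 0, 1 and 29. Its footnote and SAP 6.3.2 state no childbearing limit, and section 8 makes Table 1 binding. Only 8.2.1 limits the tests to women of childbearing potential. Tests lost: 0 if Table 1 governs or if 8.2.1 is read with 11.3.1; 3 only if 8.2.1, read with criterion 4, overrides Table 1.

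**The case against.** The strongest reply is that Appendix 3 is protocol text, 11.3.1 defines the very term that triggers criterion 5, and section 8 allows no waivers. A reader might infer from the conflict that a site exempting the woman and a site refusing to do so both comply fully. The documents do not support that: the exempting site follows criterion 4 but not 11.3.1. What stands is narrower. The eligibility text permits the exemption and gives the site no reason to look further.

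Second, criterion 4 is not open to any unexplained amenorrhea. The investigator must judge that no other medical cause exists. Criterion 3 asks for good general health, and exclusion 6 covers ongoing work-up of an undiagnosed illness. Section 11.3.1 advises further evaluation when fertility is unclear, and 11.3.2(a) and 11.3.1 are accompanied by a rule for HRT users whose menopausal status is in doubt. These narrow the group but do not close the gap: none requires a hormone result for the test case.

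Third, it might be inferred that 11.3.1 cannot work because LH is not scheduled. That goes too far. The section refers to the institution's own range, which suggests local testing, and 8.2.1 allows additional tests for safety reasons. No study-wide sample is needed.

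**Conclusion.** The inconsistency is real and lies in current text. Criterion 4 and 11.3.2(a) can release from criterion 5 a woman under 50 whom 11.3.1 counts as of childbearing potential. For each such woman, about 119 days from the first injection (119 to 126) carry no contraception requirement. This takes 3 months as 91 days, both injections given, and the 28-day minimum interval as binding. It measures an obligation not imposed; it is not an estimate of pregnancy risk.

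The number affected cannot be derived from the documents and is probably small. A reader might infer that these women would also go without pregnancy testing. Table 1, its unrestricted footnote and SAP 6.3.2 make that unlikely, although the limit in 8.2.1 leaves some doubt. Nor is there any effect on an endpoint, an analysis or power. The point merits correction as a low-cost safety matter. The differing treatment of tubal ligation in the surgical-sterility lists is a separate consistency matter and is not part of this finding.

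**What to change.** Have criterion 4 (5.1 and synopsis) and 11.3.2(a) refer to the age-specific rule in 11.3.1. Add that a woman under 50 without confirming LH and FSH results before the first injection is treated as of childbearing potential under criterion 5, with the urine tests already scheduled on Days 0, 1 and 29. In 11.3.1, state that the separate FSH bullet does not replace the under-50 requirement.

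Hormone testing stays optional and is needed only by a woman under 50 who seeks the exemption. The cost is amendment wording and, for her, possibly a local LH/FSH result before dosing, so the Day 0 and Day 1 visits might not be combined. Without a result she must meet the 28-day contraception or abstinence condition. If she starts only at an eligibility visit 8 days before Day 1, she is 28 - 8 = 20 days short and would have to be evaluated again later.

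The documents do not show whether enrollment is complete. If it is, the sponsor can check the eligibility records of women under 50 entered as postmenopausal and correct the wording before it is reused in Phase 3.
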